7.3 PHARMACOKINETIC ENDPOINTS

Plasma concentrations of alvocidib will be summarized by descriptive statistics, including mean, n, standard deviation, coefficient of variation, minimum, maximum, and median. Prior to analysis of study samples, the assay sensitivity, specificity, linearity, and reproducibility will be documented.

Parameters to be assessed include the time to C_{max} (Peak time, T_{max}) and the area under the plasma concentration versus time curve (AUC) from time 0 to 24 hours post-dose (AUC_{0-24}), the maximum observed plasma concentration (C_{max}), half life ($t_{1/2}$), AUC from 0 to time t (AUC_t), AUC from time 0 to infinity (AUC_{0-inf}), and clearance (CL).

Plasma PK analyses for alvocidib and known metabolites, if any, and dose proportionality will be determined during Cycle 1 on Days 8 and 9 (in patients receiving alvocidib following DEC) or Days 10 and 11 (in patients receiving alvocidib following AZA) ([Table 8](#)).

Table 8: Timing of PK Sampling during Cycle 1 of Phase 1b Study

PK Sample No.	Day (Regimen)	Timepoint in Relation to Alvocidib Administration	Window
1	D8 (DEC + ALV) /	Prior to IVI	At any time
2	D10 (AZA + ALV)	End of IVI	+10 mins
Up to 30-min wait (\pm 10 mins) ^a			
3	D8 (DEC + ALV) / D10 (AZA + ALV)	30 mins after end of IVI	\pm 10 mins
4		1 hr after end of IVI	\pm 10 mins
5		2 hrs after end of IVI	\pm 15 mins
6		4 hrs after end of IVI	\pm 15 mins
7	D9 (DEC + ALV) / D11 (AZA + ALV)	After alvocidib IVI (23 hrs after start of IVI in pts receiving hybrid dosing or start of infusion in pts receiving 30-60 min IVI)	\pm 1 hr

ALV = alvocidib; AZA = azacitidine; DEC = decitabine; IVI = IV infusion

a This wait time is only required in patients receiving DEC following alvocidib hybrid dosing (ie, 30-min IV bolus; up to 30-min wait; and then the 4-hr IVI).

7.4 PHARMACODYNAMIC ENDPOINTS

The pharmacodynamic relationship between alvocidib exposure and exploratory biomarkers will be quantified, specifically looking at the correlation between the rate of response (CR/CRI/CRmarrow/PR/HI) and BH3 profiling by flow cytometry with an emphasis on MCL-1 dependence.

The types of biomarkers to be analyzed may include, but are not limited to, nucleic acids, proteins, lipids or metabolites. Biomarker assessments may be used to assess and generate prognostic, predictive pharmacodynamics or surrogate biomarker signatures. These assessments may be explored in the context of MDS or related conditions or drugs of similar class. The results from these analyses are exploratory in nature and may not be included in a clinical study report (CSR).

Collection of peripheral blood samples for PD analyses will follow the schedules outlined in [Table 9](#) (DEC plus alvocidib) and [Table 10](#) (AZA plus alvocidib) ([Appendix E](#)).

Table 9: Timing of PD Sampling during Phase 1b and Phase 2 (Patients Receiving DEC + ALV)

PD Sample No.	Cycle/Day	Timepoint in Relation to Drug Administration	Window
1	Screening	Day -28 to Day 1 Prior to DEC infusion Prior to DEC infusion Prior to DEC infusion Prior to alvocidib IVI After alvocidib IVI (23 hrs after start of 4-hr IVI) During Study Visit During Study Visit	At any time
2	C1D1		≤10 mins prior
3	C1D3		≤10 mins prior
4	C1D5		≤10 mins prior
5	C1D8		At any time
6	C1D9		Within ±1 hr
7	C1D15		±3 days
8	C1D22		±3 days
9	C2D1	Prior to DEC infusion	At any time
10	C2D8	Prior to alvocidib IVI	At any time
11	C2D15	During Study Visit	±3 days
12	C2D28	During Study Visit	+1 / -3 days
13	C4* + D28	During Study Visit	At any time
14	EOS	During Study Visit	At any time

* Even cycles 4 and 6 and every 4 cycles thereafter (ie, Cycle 10, Cycle 14, etc).

DEC = decitabine; EOS = end of study; IVI = IV infusion

Table 10: Timing of PD Sampling during Phase 1b and Phase 2 (Patients Receiving AZA + ALV)

PD Sample No.	Visit/Day	Timepoint in Relation to Drug Administration	Window
1	Screening	Day -28 to Day 1 Prior to AZA infusion Prior to AZA infusion Prior to AZA infusion Prior to AZA infusion Prior to 30-min alvocidib IVI After alvocidib IVI (23 hrs after start of 30-60 min IVI) During Study Visit During Study Visit	At any time
2	C1D1		≤10 mins prior
3	C1D3		≤10 mins prior
4	C1D5		≤10 mins prior
5	C1D7		≤10 mins prior
6	C1D10		At any time
7	C1D11		Within ±1 hr
8	C1D15		±3 days
9	C1D22		±3 days
10	C2D1	Prior to AZA infusion	At any time
11	C2D10	Prior to alvocidib IVI	At any time
12	C2D15	During Study Visit	±3 days
13	C2D28	During Study Visit	+1 / -3 days
14	C4* + D28	During Study Visit	At any time
15	EOS	During Study Visit	At any time

* Even cycles 4 and 6 and every 4 cycles thereafter (ie, Cycle 10, Cycle 14, etc).

AZA = azacitidine; EOS = end of study; IVI = IV infusion

The samples may be retained for no longer than 20 years after study completion or per local requirements.

8. ADVERSE EVENTS

8.1 DEFINITIONS

An adverse event (AE) is defined as any untoward medical occurrence associated with the use of a drug in humans, whether or not considered drug related. An AE can therefore be any unfavorable and unintended sign (including an abnormal laboratory finding), symptom, or disease temporally associated with the use of a drug, whether or not related to the drug product.)

Suspected adverse reaction means any adverse event for which there is a reasonable possibility that the drug caused the adverse event. For the purposes of Investigational New Drug (IND) safety reporting, 'reasonable possibility' means there is evidence to suggest a causal relationship between the drug and the adverse event.

Unexpected adverse event or unexpected suspected adverse reaction: An adverse event or suspected adverse reaction is considered unexpected if it is not listed in the current [Investigator's Brochure](#) or is not listed at the specificity or severity that has been observed; or, is not consistent with the risk information described in the general investigational plan (clinical study protocol).

Toxicities will be assessed according to the NCI CTCAE v5.0 (see [Appendix D](#)). When the NCI CTCAE grade is not available, the investigator will use the following toxicity grading: mild, moderate, severe, life-threatening or fatal.

- GRADE 1 – Mild:
 - Transient or mild discomfort; no limitation in activity; no medical intervention/therapy required.
- GRADE 2 – Moderate:
 - Mild to moderate limitation in activity - some assistance may be needed; no or minimal medical intervention/therapy required.
- GRADE 3 – Severe:
 - Marked limitation in activity, some assistance usually required; medical intervention/therapy required, hospitalizations possible.
- GRADE 4 – Life Threatening:
 - Extreme limitation in activity, significant assistance required; life threatening (immediate risk of death); significant medical intervention/therapy required, hospitalization or hospice care probable.
- GRADE 5 – Fatal
 - Results in death.

8.2 CAUSALITY

Relationship of the adverse event (AE) to the study drug should be defined as follows:

- Unrelated:
 - AE is *clearly not related* to the investigational agent(s)
- Unlikely:
 - AE is *doubtfully related* to the investigational agent(s)
- Possibly:
 - AE *may be related* to the investigational agent(s)
- Probably:
 - AE is *likely related* to the investigational agent(s)
- Definitely:
 - AE is *clearly related* to the investigational agent(s)

8.3 SERIOUS ADVERSE EVENTS

A serious adverse event (SAE) is defined as any experience that suggests a significant hazard, contraindication, side effect, or precaution. An SAE includes:

- Any death, or
- Any life-threatening event (ie, the patient is at immediate risk of death from the event as it occurred), or
- Any event that is persistently, significantly, severely or permanently disabling, or requires intervention to prevent such disability, or
- Any event which requires inpatient hospitalization or prolongs hospitalization, or
- Any congenital abnormality/birth defect, or
- Any medically significant event that may jeopardize the patient or may require intervention to prevent one of the other outcomes listed above.

In addition, any adverse event which results in termination of the patient from study will be considered a potentially serious adverse event and must be reported to the Sponsor as described in [Section 8.4](#).

Bone marrow suppression and associated complications are seen as part of the spectrum of underlying MDS and are expected events during MDS therapy. Therefore, myelosuppression and associated complications directly related to the myelosuppression, such as fever, febrile neutropenia, infections, anemia, thrombocytopenia, and bleeding, will not be reported as serious adverse events (SAEs) but will be reported as AEs on the AE CRF and will be summarized in the updated and final reports.

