4.5.2 Management of Hematologic Toxicities

Bone marrow suppression and associated complications are expected events during MDS therapy and are part of the treatment process (marrow emptying of abnormal cells). Therefore, hospitalization or prolongation of hospitalization for myelosuppression and associated complications directly related to the myelosuppression, such as fever, infections and bleeding, will not be reported as serious adverse events (SAEs), but will be reported as adverse events on the adverse event case report form and will be summarized in the updated and final reports.

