8.7 PATIENT DEATHS

Every effort will be made in the case of patients who die to determine the cause of death. Information regarding a patient who dies more than 30 days after receiving study drug may be recorded on a Death Report Form (no SAE report is required). An SAE report is recorded only if the event leading up to the patient's death began within 30 days of the last administration of study drug.

The Death Report Form is distinct and separate from the adverse event form included in the case report form.

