## **12.2 Serious Adverse Events**

Serious adverse events will be obtained from the AE dataset where any of the Seriousness Criteria of 1-6 is checked (note: AESAE criteria 7 = NOT serious).

Planned Serious TEAE summary tables include:

- Incidence of Serious Treatment-Emergent Adverse Events by MedDRA System Organ Class and Preferred Term (Safety Population)
- Incidence of Serious Treatment-Emergent Adverse Events Judged Possibly, Probably or Definitely Related to the Study Drug Regimen by MedDRA System Organ Class and Preferred Term (Safety Population)
- Treatment-Emergent Adverse Events in the Standardized MedDRA Query for Tumor Lysis Syndrome Judged Possibly, Probably or Definitely Related to the Study Drug Regimen by MedDRA Preferred Term (Safety Population)

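### Protocol 8.3 excludes complications of myelosuppression from SAE reporting whatever their outcome, in conflict with its own death and life-threatening criteria and with 4.5.2 and 8.7

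*Protocol*

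**What the plan says.** Protocol 8.3 lists the SAE criteria. The first is death, without qualification. The second reads "Any life-threatening event (ie, the patient is at immediate risk of death from the event as it occurred), or". The list also includes inpatient admission or a longer stay. Below the list, 8.3 adds that "any adverse event which results in termination of the patient from study will be considered a potentially serious adverse event" and must go to the Sponsor.

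The last paragraph of 8.3 then makes an exemption for marrow suppression and whatever follows directly from it, with infections and bleeding among the examples. Events of this kind "will not be reported as serious adverse events (SAEs) but will be reported as AEs on the AE CRF". It gives no exception by grade, outcome or seriousness criterion.

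Protocol 4.5.2 makes a similar exemption with a different subject. There it is "hospitalization or prolongation of hospitalization for myelosuppression and associated complications directly related to the myelosuppression" that is not reported as an SAE.

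Protocol 8.7, on deaths, says "An SAE report is recorded only if the event leading up to" the death began within 30 days of the last administration. It makes no exception for deaths related to myelosuppression.

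Protocol 8.5 sets the 24-hour clock. It starts for an SAE, for an unexpected AE of Grade 3 or higher, and for an AE that permanently ends study drug. For the last of these, the SAE form is required even if the event is not serious.

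SAP 12.2 says: "Serious adverse events will be obtained from the AE dataset where any of the Seriousness Criteria of 1-6 is checked".

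**The concern.** The same exemption appears twice with two scopes. In 4.5.2 it removes one ground for seriousness, hospitalization. In 8.3 it removes the event class altogether. Fatal neutropenic sepsis is therefore an SAE under the 8.3 criteria and 8.7, but not under the last paragraph of 8.3.

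Two things are at stake. One is prompt notice to the Medical Monitor of the most severe infections and bleeds. The other is whether the SAE tables mean the same thing at every site, since they depend on what each site ticked.

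**Working it through.** The plan gives no figure to reproduce. The check sets the provisions side by side for four kinds of event, each assumed to be judged a direct complication of myelosuppression.

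| Event | 8.3 criteria | 8.3 last paragraph | 4.5.2 | 8.7 | 24-hour route in 8.5 |
|---|---|---|---|---|---|
| Admission only | SAE | Not SAE | Not SAE | Not relevant | Only if unexpected and Grade 3 or higher |
| Life-threatening, treatment continues | SAE | Not SAE | Outside the exemption | Not relevant | Lost, unless unexpected |
| Fatal, onset within 30 days of last dose | SAE | Not SAE | Outside the exemption | SAE report | Depends on the section followed |
| Permanently ends study drug, no listed criterion met | Not on the list (potentially serious if it ends participation) | Not SAE | Not addressed | Not relevant | Report and SAE form required regardless |

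In the first row, 8.3's last paragraph and 4.5.2 agree. In the second and third rows they do not.

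**Second row, trigger by trigger.**
1. SAE status is removed by the last paragraph of 8.3.
2. Permanent discontinuation is not met, because treatment continues.
3. For the unexpected-event trigger, 8.3 calls these complications expected. Protocol 8.1, however, judges expectedness against the Investigator's Brochure, including the severity listed there. The Brochure is not among the documents, so this trigger may or may not apply.

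The protocol foresees such cases: 4.5.1.4 and 4.6.2.2 both provide for neutropenic patients with life-threatening infection.

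**Effect on the SAE tables.** Cohort sizes in SAP 8.1 are 3, 3, 3, 4, 3 and 4, which sum to 20. One patient coded differently changes the SAE proportion by 1/3 = 33.3 percentage points in a cohort of 3, by 1/4 = 25 points in a cohort of 4, and by 1/20 = 5 points overall.

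**Can the exempted class include serious outcomes?** Protocol Table 4 reports neutropenic fever or infection in 14/24 = 58.3% of patients in the alvocidib monotherapy study (stated as 58%). It attributes 5/6 = 83% of the early deaths described in the first 27 patients of Study 6 to septic shock and multi-organ failure. These figures come from acute leukemia, the second from a combination with cytarabine and mitoxantrone. They show that such events can be fatal; they give no rate for this trial.

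**The case against.** Exempting expected complications of marrow suppression from SAE reporting may be deliberate, and several safeguards remain. The events stay on the AE CRF with their grade, and Protocol 8.4 asks for seriousness to be described. SAP 12.1 plans all-TEAE tables and Grade 3-5 tables. Protocol 4.5.3 makes a Grade 5 toxicity in Cycle 1 a DLT unless it is clearly due to disease or outside causes, and 11.10.1 tabulates deaths on study. Table 7 calls for Medical Monitor review before a patient with a Grade 4 drug-related AE continues. The discontinuation route in 8.5 may also catch many fatal events. All of this stands, so the events are not lost. But the Table 7 review carries no 24-hour clock, and none of these safeguards settles which scope of the exemption applies.

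Three stronger readings are tempting, and the documents do not support them.

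- A reader might infer that treatment-ending infections and bleeds also escape prompt reporting. They do not: 8.5 requires the 24-hour report and the SAE form for any AE that permanently ends study drug, serious or not. Section 8.3 calls participation-ending events only potentially serious.
- A reader might infer from Table 4 that infection caused most earlier deaths, by adding 2 of 4, 3 of 3, 1 of 1, 5 of 5 and 5 of 6 to get 16 of 19. Studies 2 and 5 name infection together with multi-organ failure without a split by death. Study 6 reports 10 deaths, of which only 6 are described; with all 10 the sum is 16 of 4 + 3 + 1 + 5 + 10 = 23, with four causes not given. Attribution to myelosuppression would be a further assumption.
- A reader might infer that SAE rates by cohort cannot be interpreted. The risk is that coding differs between sites. Nothing shows that it did, and the analysis is descriptive only.

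The study's closure also limits the value of new protocol text. It does not affect the data query, since the SAP was written for a lock still to come.

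**Conclusion.** The point holds for fatal and life-threatening events. The last paragraph of 8.3 contradicts that section's own criteria, the narrower exemption in 4.5.2, and 8.7. The clearest practical gap is a life-threatening infection or bleed after which the patient stays on treatment. Fatal events are inconsistently handled rather than plainly unreported. Discontinuation events are not part of the gap.

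The number of affected events among the 20 patients is unknown. What can be stated is the sensitivity of the SAE tables: 25 to 33.3 percentage points per cohort for one patient coded differently.

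This rests on three assumptions: that sites judge such events to be direct complications of myelosuppression; that 4.5.2 removes hospitalization as a ground for seriousness, not every event that involves an admission; and, for the 24-hour gap, that the Investigator's Brochure already lists these events at the severity seen.

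**What to change.** Reconcile the last paragraph of 8.3 with 4.5.2, 8.5 and 8.7. The exemption should cover the hospitalization criterion only, and the text should say that a fatal or life-threatening complication of myelosuppression remains an SAE with 24-hour reporting. In the same edit, correct the cross-reference in 8.3: it sends participation-ending events to 8.4 for Sponsor reporting, but the procedure is in 8.5.

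Before lock, query the AE data of the 20 patients for Grade 4-5 infection, bleeding and febrile neutropenia with no seriousness criterion ticked. Ask sites to confirm which events meet the death or life-threatening criterion, and include those in the SAP 12.2 tables. Do not add discontinuation events to the SAE tables unless they meet a seriousness criterion in 8.3.

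The cost is one paragraph, one data query and a few more SAE reports.

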8.4 ELICITING AND REPORTING ADVERSE EVENTS

All adverse events, regardless of severity, which occur during the study, will be documented in the study progress notes, and the "Adverse Event" case report form will be completed. This includes both serious and non-serious events. Adverse events occurring from the time of the first dose will be captured.

All adverse events noted by study staff or volunteered by study patients at any time will be recorded. The PI or a qualified designated staff physician will conduct clinical assessments of all patients at each scheduled clinic visit. In addition, patients will be queried about any adverse symptoms they have experienced since the previous study visit. In order to avoid bias in eliciting events, suggestive questioning of the patients shall not occur.

A laboratory abnormality will be reported on the "Adverse Event" case report form only if it is the main causative factor of an SAE, requires a therapeutic intervention, is the reason for a patient coming off study, or meets DLT criteria. Record the highest grade of the laboratory abnormality with start and stop dates associated with that grade. Laboratory values for hematology and serum chemistry parameters will be collected during the time the patient is on study to facilitate duration of worst CTCAE grade per cycle change-from-baseline analyses and overall worst CTCAE grade during the study. Any laboratory parameters assessed outside the per-protocol visits (ie, interim labs) will be recorded as 'Unscheduled Laboratory Assessments' in the database.

Adverse events will be reported and described in terms of intensity, seriousness and causality, based on the PI's judgment using protocol-defined definitions. Necessary counter measures will also be reported on the appropriate case report form used to collect concomitant medications.

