4.5.3 Dose-limiting Toxicities

Dose-limiting toxicities (DLTs) will be determined during Cycle 1 and defined as follows based on the NCI CTCAE v5.0:

- Any Grade 5 toxicity that is not clearly and incontrovertibly related to the underlying disease or extraneous causes
- Any Grade 4 nonhematologic toxicity considered at least possibly drug related
- Grade 4 neutropenia lasting ≥ 42 days from the start of a cycle in the absence of evidence of active disease
- Any AST or ALT elevation $\geq 3 \times$ ULN accompanied by serum bilirubin levels $> 2 \times$ ULN
- Any Grade 3 nonhematologic toxicity considered at least possibly drug related and that does not resolve to \leq Grade 2 within 48 hours, with the following exceptions:
 - Grade 3 bilirubin, AST, ALT or alkaline phosphatase will be considered dose-limiting only if resolution to \leq Grade 2 requires more than 7 days

- Grade 3 diarrhea, mucositis, nausea, or vomiting will be considered dose limiting only if resolution to \leq Grade 2 (including use of supportive care) requires more than 7 days
- \geq Grade 3 creatinine elevation that does not resolve to \leq Grade 2 within 7 days
- Anorexia, fever, neutropenic fever, and infections of any grade
- Bone marrow hypoplasia that occurs for >42 days with bone marrow (BM) cellularity $\leq 5\%$ and no evidence of MDS/leukemia. Bone marrow disease assessments conducted per protocol on Day 28 (± 3 days) of every even cycle may be used to guide this decision.

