### **12.1 Treatment Emergent Adverse Events**

Treatment-emergent adverse events (TEAEs) are defined as all AEs that begin on or after the date of the first administration of study drug. Related AEs are those reported as possibly related, probably related, or related to study drug. The verbatim terms of the Treatment Emergent Adverse Events (TEAE) will be coded to preferred terms (PT) and system organ

classes (SOC) per MedDRA® (Medical Dictionary for Regulatory Activities) Version 21.0 (or later).

All reported AEs (including non-TEAEs) will be listed, documenting all information collected on the eCRF including verbatim term, MedDRA preferred term, MedDRA system organ class, start date, stop date, severity and relationship to study drug, action taken, and outcome.

The TEAEs will be graded by the Investigator in terms of:

- Severity graded 1-5 according to CTCAE v5.0:
  - 1=Mild, 2=Moderate, 3=Severe, 4= Life Threatening, 5=Fatal.
- Relation to study drug:
  - ‘Related’ includes events where the causality was reported as ‘Possibly Related’, or ‘Probably Related’, or ‘Definitely Related’, or where the relationship was not reported on the eCRF.
  - ‘Not Related’ includes events where the study drug causality was reported as ‘Unrelated’ or ‘Unlikely Related’ on the eCRF.

All TEAE summary tables will be presented with the number and percentages of patients in the Safety population. An overall summary of TEAEs will be tabulated by treatment regimen, relation to study treatment, and grade. In addition, TEAEs will be summarized by system organ class (SOC) and preferred term (PT).

Planned TEAE summary tables include:

- Overall Summary of Treatment-Emergent Adverse Events (Safety Population)
- Incidence of Treatment-Emergent Adverse Events by MedDRA System Organ Class and Preferred Term (Safety Population)
- Incidence of Treatment-Emergent Adverse Events by MedDRA System Organ Class, Preferred Term, and CTCAE Severity Grade (Safety Population)
- Incidence of Treatment-Emergent Grade 3, Grade 4, and Grade 5 Adverse Events by MedDRA System Organ Class and Preferred Term (Safety Population)
- Incidence of Treatment-Emergent Grade 3, Grade 4, and Grade 5 Adverse Events by MedDRA System Organ Class and Preferred Term and CTCAE Severity Grade (Safety Population)

- Incidence of Treatment-Emergent Adverse Events Judged Possibly, Probably or Definitely Related to the Study Drug Regimen by MedDRA System Organ Class and Preferred Term (Safety Population)

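### Protocol 8.3 and 8.4 give different rules for putting uncomplicated cytopenias on the AE form, so cytopenia rates in the SAP 12.1 tables can depend on site practice

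*Protocol*

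**What the plan says.** Protocol 8.3 states that myelosuppression and its direct complications (anemia and thrombocytopenia are among those named) "will not be reported as serious adverse events (SAEs) but will be reported as AEs on the AE CRF and will be summarized". It attaches no grade, duration or treatment threshold. Protocol 4.5.2 has a parallel statement, but there the subject is hospitalization for myelosuppression and its complications.

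Protocol 8.4 restricts the same form. A laboratory abnormality is entered "only if it is the main causative factor of an SAE, requires a therapeutic intervention, is the reason for a patient coming off study"; the fourth condition is meeting DLT criteria. The four conditions are alternatives, so any one admits the event.

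Protocol 8.1 says that an abnormal laboratory finding can itself be an adverse event, so a low count falls under both sections. The DLT criterion for neutropenia in protocol 4.5.3 requires Grade 4 lasting at least 42 "days from the start of a cycle in the absence of evidence of active disease".

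On analysis, protocol 11.10.2 plans CTCAE shift tables of laboratory values, and SAP 3.7.1 still mentions shift tables. The operative SAP 12.3 puts safety laboratory data in patient listings only, and SAP 16 says that the SAP supersedes the protocol's statistical considerations. SAP 12.1 tabulates TEAEs, Grade 3 to 5 TEAEs and related TEAEs from the AE records.

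**The concern.** A neutrophil, hemoglobin or platelet count that falls without treatment, withdrawal or a DLT is to be recorded under the plain wording of 8.3 and left off under 8.4. No section exempts cytopenias from 8.4 or gives either rule precedence, so two sites can handle the same event differently and each can cite the protocol.

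The SAP leaves no tabulated backstop. With laboratory data only listed, the AE-based tables in SAP 12.1 are the only operative by-cohort tabulation of cytopenias, and SAP 9.1 pools the sites. For an expected toxicity of this regimen, the tabulated rate could partly reflect reporting habit. The three lineages could also enter the table on different thresholds, because low hemoglobin and platelets are commonly answered with a transfusion, while routine growth factor for neutropenia is not allowed (protocol 4.6.2.2).

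**Working it through.** The plan states no figure to reproduce. The check sets the two rules side by side and then sizes one reclassified patient.

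**Step 1: the four conditions of 8.4, applied to neutropenia.**
- Main cause of an SAE: largely closed, because 8.3 keeps myelosuppression and its direct complications out of SAE reporting.
- Therapeutic intervention: narrow for growth factor, which 4.6.2.2 limits to life-threatening infection with ongoing neutropenia and Medical Monitor approval. Section 8.4 does not define the term, so other treatment could also count.
- Reason for coming off study: open. Protocol 6.2 lists excessive Grade 3-4 toxicity and laboratory abnormalities as grounds for withdrawal, but this reaches only patients who leave.
- DLT criteria: narrow. Grade 4 must persist to 42 days counted from the start of the cycle, without active disease.

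**Step 2: the rules by situation.** A transfusion is taken to be a therapeutic intervention (assumption).

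| Situation | 8.3 as worded | 8.4 |
|---|---|---|
| Grade 4 neutropenia, untreated, resolves before Day 42 of the cycle, patient stays on study | AE | not entered |
| Anemia or thrombocytopenia, not transfused, patient stays on study, no DLT | AE | not entered |
| Anemia or thrombocytopenia, transfused | AE | AE |
| Cytopenia that ends participation | AE | AE |
| Cytopenia meeting DLT criteria | AE | AE |
| Febrile neutropenia, infection, bleeding | AE | AE (clinical events, outside the laboratory limit) |

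Only the first two rows differ.

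**Step 3: size.** Cohorts have 3 or 4 patients and the total is 20 (SAP 1 and 8.1). One patient counted under one rule but not the other moves a rate by 1/n:
- 1/3 = 33.3 points
- 1/4 = 25.0 points
- 1/20 = 5.0 points

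For the total, let k be the patients with a laboratory cytopenia and q the share of them meeting an 8.4 condition. The gap between the rules is k(1 − q)/20. The documents give neither k nor q, so the values below are assumptions.

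| k of 20 | Rate under 8.3 | Gap, q = 0 | Gap, q = 0.5 | Gap, q = 1 |
|---|---|---|---|---|
| 5 | 25% | 25 points | 12.5 | 0 |
| 10 | 50% | 50 points | 25 | 0 |
| 15 | 75% | 75 points | 37.5 | 0 |

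The q = 0 column is an extreme: no affected patient meets any condition and every site follows 8.4.

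**The case against.** The strongest reply is that 8.3 sits under the heading of serious adverse events and may settle only whether an event is an AE or an SAE. Section 4.5.2, which speaks of hospitalization for myelosuppression, supports that. On this reading 8.4 sets the threshold for laboratory values and a site can follow both sections. A reader might infer that the two rules cannot both be obeyed; the documents do not force that. What stands is that they do not choose this reading either, and 8.3 as worded covers myelosuppression without reference to hospitalization.

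A reader might also infer that any Grade 4 neutropenia of up to 41 days escapes 8.4. The 42 days run from the start of the cycle, so that holds only for onset on Day 1. Neutropenia starting on Day 10 and lasting 41 days covers Days 10 to 50 (10 + 41 − 1 = 50). It passes Day 42 and, without active disease, meets the DLT criterion.

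It is fair to add that the laboratory data are not lost. Protocol 8.4 itself has hematology values collected for worst-grade analyses, and the SAP lists them. This limits the harm to the tables and makes the repair cheap. The analysis is also descriptive only (SAP 15.1), so no test result is at risk.

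**Conclusion.** The two sections leave open whether an uncomplicated cytopenia belongs on the AE form, and the SAP provides no laboratory-based table that would make the answer immaterial. The effect is confined to the TEAE, Grade 3 to 5 and related-TEAE tables, at the per-patient sizes shown. How many patients are affected cannot be told from the documents.

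Three stronger conclusions are not supported:
- That neutropenia is in fact under-counted, or tabulated at 0%. This needs the extreme case above.
- That the cohorts are not comparable. The documents do not say which sites enrolled which cohorts, or which section any site followed.
- That dose decisions are compromised. Events meeting DLT criteria are recorded under both sections, so the MTD and SPRT rules are untouched.

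The conclusion rests on reading an isolated low count as a laboratory abnormality under 8.4, which 8.1 supports, and on treating a transfusion as a therapeutic intervention.

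**What to change.** Sites were told of study closure on 17 November 2020 and no Expansion or Phase 2 patients were enrolled (SAP 1 and 2), so a new protocol sentence would change nothing prospectively. The repair belongs in the SAP and in data cleaning before database lock.

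1. State in SAP 12.1 one rule for cytopenias in the TEAE tables: a post-baseline neutropenia, anemia or thrombocytopenia counts when it has worsened in CTCAE grade from baseline to Grade 3 or higher. Present this as the SAP's own rule, since 8.3 contains no threshold. The comparison with baseline keeps unchanged pre-existing cytopenias out. Footnote that Grade 1-2 cytopenia records are not reconciled.
2. For all 20 patients, run an edit check with the same threshold. List each such event in the hematology data that has no matching AE record, and query it. The query should state the rule, or a site could answer it by citing 8.4.
3. Tabulate worst post-baseline hematology grade against baseline grade by cohort from the laboratory data, as protocol 11.10.2 planned. Include unscheduled values, which SAP 8.4 allows in summaries that are not time-specific. This table does not depend on AE reporting.

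The cost is some site queries, one more table and higher reported cytopenia rates. No new data collection from patients is needed.
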